9.3. VARIABLES

9.3.1. Disease definitions

Definite AF will be defined as a hospitalisation with an AF diagnosis (primary, linked, or associated, I48 ICD-10 code) or a procedure for AF (cardioversion, catheter ablation), or a Long-Term Disease (LTD) registration for AF (I48 ICD-10 code) in the 36 months before the index date or within six months after index date.

Probable AF will be defined as subjects without definite AF, and with anticoagulant and amiodarone or dronedarone co-prescription, or having a high probability of AF, using an AF disease score based on a logistic regression of the definite AF population with the following parameters (see statistical analysis):

- Gender and age of the subject at index date,
- Cardiologist or hospital physician prescriber of the first DOAC or VKA dispensation,
- Investigation within 2 months before index date: Holter ECG monitoring or echocardiography, T3-T4 thyroid hormone test, D-dimer test or venous echodoppler,
- ≥ 1 drug dispensation within 3 months before index date for acetylsalicylic acid (ASA), ASA in association, clopidogrel, fondaparinux, heparin or low-molecular-weight heparin (LMWH),
- ≥ 1 drug dispensation within 2 months before or 2 months after index date for sotalol, other beta-blockers excluding associations, beta-blockers in association, verapamil or diltiazem, digoxin or digitoxin, other antiarrhythmic drug, other calcium channel blocker, agents acting on the renin-angiotensin system, diuretic.

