- The study follow-up period will start on the study index date and will end two years later, or until the date of death with a right censoring on 31 December 2015 (at least a one-year follow-up period except for death).
- Rivaroxaban, dabigatran, or VKA exposure will be defined during the study follow-up period, as well as the occurrence of each of the study outcome.

The overall design of the study is presented in the following figure.

POPULATION Subjects with a first reimbursed dispensation of rivaroxaban (15 or 20 mg),

dabigatran (110 or 150 mg), or VKA in 2013 or 2014 and no previous anticoagulant dispensation during the previous three years, with a specific or sensitive diagnosis of non-valvular AF (NVAF). Two NVAF cohorts will be defined:

- Specific NVAF cohort (for the main analysis) will include definite NVAF subjects as defined below (to minimize the risk of false positives);
- Sensitive NVAF cohort (as secondary analysis) will include definite NVAF and probable NVAF subjects as defined below (to minimize the risk of false negatives).

Definite NVAF subjects: Definite AF information in the database, and no other indication for the use of anticoagulant (treatment of venous thromboembolic events (VTE), prevention of VTE after orthopaedic surgery), or history of rheumatic valve disease or valve replacement.

Probable NVAF subjects: Probable AF information in the database (using the development of an AF disease score), and no other indication for use of anticoagulant (treatment of VTE, prevention of VTE after orthopaedic surgery), or history of rheumatic valve disease or valve replacement.

VARIABLES

Disease definition

- Definite AF: Hospitalisation with an AF diagnosis (primary, linked or associated) or a procedure for AF (cardioversion, catheter ablation), or a Long-Term Disease (LTD) registration for AF in the 36 months before the index date or within six months after index date.
- Probable AF: Subjects without definite AF, and with anticoagulant and amiodarone or dronedarone co-prescription, or having a high probability of AF, using an AF disease score based on a logistic regression of the definite AF population with the following parameters (see statistical analysis):
 - Gender and age of the subject at index date,
 - Cardiologist or hospital physician prescriber of the first DOAC or VKA dispensation,

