9. RESEARCH METHODS

9.1. STUDY DESIGN

The design is a cohort study in a healthcare claims and hospitalisation database including new users of rivaroxaban, dabigatran, or VKA for SPAF with a follow-up for at least one year and up to two years per subject. The overall design of the study is presented in the following figure (Figure 1).

Data will be extracted from 1 January 2010 to 31 December 2015. The index date will be the first reimbursed dispensation of rivaroxaban, dabigatran, or VKA in 2013 or 2014, without dispensation of any of them within the 3 years before index date. The study follow-up period will start on the study index date and will end two years later, or until the date of death with a right censoring on 31 December 2015 (at least a one year follow-up period except for death). Rivaroxaban, dabigatran, and VKA exposure will be defined during the study follow-up period, as well as the occurrence of each of the study outcome.

The main advantages of this study are that data are collected independently of the research question, allowing the conduct of a nationwide population-based historical cohort. Limits of database analyses are discussed later (Section 9.9 Limitations of the research methods).

[figure not shown]

Figure 1: Study design

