- Hospital-discharge summaries from the PMSI: ICD-10 diagnosis codes (primary, linked and associated diagnosis) for all medical, obstetric and surgery hospitalisations, with the date and duration, medical procedures and cost coding system. The hospital discharge summary includes the medical unit summaries when the patient is hospitalized successively in several medical units.

³ Caisse Nationale de l'Assurance Maladie des Travailleurs Salariés (French national health insurance fund for salaried workers)

⁴ Mutuelle Sociale Agricole (French national health insurance fund for farmers and agricultural workers)

⁵ Régime Social des Indépendants (French national health insurance fund for independent workers)

Primary diagnosis is the health problem that motivated the admission in the hospital. It is determined at hospital discharge. For patients hospitalized successively in several medical units, the primary diagnosis of the hospitalisation, as well as all medical unit primary diagnoses, are generally taken into account to define the occurrence of an outcome in a pharmacoepidemiology study.

A linked diagnosis can exist only if the primary diagnosis is a care procedure with a code Z of the ICD-10 classification (e.g. chemotherapy session) for a chronic or LTD disease. It indicates the pathology at the origin of the care procedure. Linked diagnoses can be used to define chronic diseases but are generally not taken into account to define the occurrence of an outcome in a pharmacoepidemiology study (many being false positives for the studied outcome).

Associated diagnoses are specified if they represent specific healthcare resources. They are mainly underlying chronic diseases. Associated diagnoses can be used to define chronic diseases but are generally not taken into account to define the occurrence of an outcome in a pharmacoepidemiology study (many being false positives for the studied outcome).

The CNAMTS proposes algorithms to define 56 diseases (CNAMTS 2015), including stroke and ACS. Furthermore, ICD-10 code validation in the SNIIRAM was recently published for ACS and stroke (Bezin 2015, Giroud 2015), and others validation works are on-going.

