9.9. LIMITATIONS OF THE RESEARCH METHODS

The SNIIRAM is a national healthcare claims database linked to the national hospital discharge summaries database that covers more than 95% of the French population. It provides a unique opportunity to identify all new users of DOAC or VKA in NVAF in 2013-2014, with exhaustive information about reimbursed treatments out of hospital and use of reimbursed healthcare resources, as well as all hospitalisations for the outcomes of interest. Furthermore, the SNIIRAM has the advantage of any study extracting patient records from an existing database that are not impacted by the study.

This is also the main limit of this claims and hospitalisation database that was built for administrative and reimbursement purposes with a lack of clinical data and biological results, including some risk factors such as smoking status, body mass index, blood pressure, and cholesterol values, that could be impact the patient prognosis. However, statistical methods such as PS and hdPS were developed to improve control of confounding using a large number of covariates ascertained from patients' healthcare claims data, as these variables may collectively be proxies for unmeasured confounders (Schneeweiss 2009, Rassen 2012).

Selection bias

Since all subjects identified with extraction criteria in 2013-2014 will be extracted from a national database, there is no study selection bias, nor attrition bias, except very rare withdrawals from one of the healthcare insurance systems including and covering more than 95% of the French population.

Information bias

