- **AF indication:** Anticoagulants are prescribed for several medical conditions. The main analysis will be done using the specific NVAF population, with a highly specific definition of the disease (LTD for AF or a hospitalisation with an AF diagnosis before the index date). Nevertheless, several subjects with an AF do not have an LTD and are not hospitalized or hospitalized for another primary diagnosis without AF reported in the linked or associated diagnosis, during the 3 years before index date. To assess the robustness of the main analysis results, secondary analyses will be performed using a sensitive definition for NVAF (sensitive NVAF population) defined as the subjects of the specific NVAF population, plus those with probable information using an AF disease score. In terms of bias, there is no reason that the specificity of AF definition will be different according to the treatment group.
- **Drug exposure:** VKA and DOAC exposure will be assessed using exhaustive non-hospital drug claims. Drugs prescribed during hospital stays are not recorded and could represent a potential risk of exposure underestimation. However, it should concern few subjects for a very short period of time, and the impact over a 3-year study period should be negligible. Drug expose is defined as the time between index date and the end of follow-up for subjects without drug withdrawal, i.e. as the time between index date and last dispensation + 90 days (30 days for the duration of the

last dispensation or less for small DOAC packaging, plus a grace period of 60 days), or before in case of drug switch. Two grace periods will be considered (60 and 30 days) to estimate the true drug withdrawal, in order to take into account the drug supply in real life, or short discontinuation and bad drug adherence that could be a risky situation for ischemic event, directly in relation with the use of the DOAC or VKA. This would also cover short hospital stays.

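### Definite AF can be established up to six months after the index date, so an early outcome stay can itself admit a patient to the main cohort; incidence is biased, and hazard ratios are biased only if the arms differ

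*Protocol*

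**What the plan says.** The main analysis uses one cohort: "Specific NVAF cohort (for the main analysis) will include definite NVAF subjects as defined below" (Protocol, section 4; repeated in 9.2). Section 9.3.1 opens its definition with "Definite AF will be defined as a hospitalisation with an AF diagnosis (primary, linked, or associated, I48 ICD-10 code". It adds AF procedures and long-term disease (LTD) registration for AF, and sets the window as "in the 36 months before the index date or within six months after index date". The abstract gives the same window.

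Time zero is the first dispensation. Section 9.1 states: "The study follow-up period will start on the study index date and will end two years later". Section 9.3.3 also starts exposure at the index date. Section 9.3.4 defines stroke/SE, bleeding and ACS as hospital stays identified by primary diagnosis.

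Section 9.9, under AF indication, describes the same main analysis differently, as done "with a highly specific definition of the disease (LTD for AF or a hospitalisation with an AF diagnosis before the index date". It does not mention the six months after index.

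**The concern.** Membership of the main cohort can depend on what happens during follow-up. Take two patients with AF, neither with an AF record before index. One has a stroke in month two and the stay lists AF as an associated diagnosis: that patient enters and contributes an event. The other has no stroke and acquires no AF record within six months: that patient is left out of the main cohort. Selecting on early events in this way raises early incidence of stroke, bleeding and ACS.

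For death the selection runs the other way. A patient without a pre-index record who dies before any AF record cannot enter.

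Cumulative incidence and incidence rates are objectives in section 8, so this matters even without an effect on the treatment comparisons. The hazard ratios are also at risk if the arms differ in how many patients enter through the post-index window.

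**Working it through.** **1. The text.** Sections 9.3.1 (I48 in any position, up to six months after index), 9.1 and 9.3.3 (time zero at index) and 9.3.4 (outcome is a stay by primary diagnosis) together allow one stay to be both the qualifying record and the event. Sections 9.1 to 9.3.4 contain no landmark, no delayed entry and no rule against outcome stays as qualifying records. The sensitivity analyses in 9.7.1 vary the grace period, the cohort and a bleeding classification. None changes the AF window, and the sensitive cohort contains all definite subjects. Section 9.3.1 conflicts with section 9.9.

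**2. Size among patients who enter only after index.** The protocol states no figure for this, so there is none to reproduce.

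- From section 9.5: stroke/SE rate on VKA 1.6 per 100 PY. It is used here as the true rate, for illustration.
- Assumed: *q*, the share of AF patients without a prior record who acquire one by a non-outcome route within six months, 40%; *c*, the share of stroke stays coded with AF, 90%.

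Six-month risk: r = 1 − exp(−0.016 × 0.5) = 0.80%.

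P(included | stroke) = q + (1 − q)c = 0.4 + 0.6 × 0.9 = 0.94. P(included | no stroke) = q = 0.40.

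Risk among those included = 0.0080 × 0.94 / (0.0080 × 0.94 + 0.9920 × 0.40) = 1.85%, or 2.3 times the true risk.

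**3. Effect on a hazard ratio.** Suppose further that 10% of one arm and 20% of the other enter after index, and that the true hazard ratio is 1. An arm's six-month inflation is 1 + f × (2.325 − 1), with f the share entering after index.

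- f = 10%: 1.13; f = 20%: 1.26 to 1.27.
- Six months: 1.1325 / 1.265 = 0.90.
- One year (selection acts in one of two half-years): (1.1325 + 1) / (1.265 + 1) = 0.94.
- Two years (one of four half-years): (1.1325 + 3) / (1.265 + 3) = 0.97.
- Equal f and equal coding: 1.

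The same formulas over a wider grid, with the 10% versus 20% contrast held fixed:

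| q | c | Risk relative to truth, post-index entrants | HR, 6 months | HR, 1 year | HR, 2 years |
|---|---|---|---|---|---|
| 20% | 90% | 4.5 | 0.80 | 0.87 | 0.93 |
| 40% | 90% | 2.3 | 0.90 | 0.94 | 0.97 |
| 40% | 30% | 1.4 | 0.96 | 0.98 | 0.99 |
| 60% | 60% | 1.4 | 0.96 | 0.98 | 0.99 |
| 60% | 30% | 1.2 | 0.98 | 0.99 | 0.99 |

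Reversing the arms inverts the ratios. These one- and two-year values assume a constant hazard. On-treatment censoring would weaken the dilution somewhat.

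**4. Whole-cohort rates by simulation.** Three million patients per scenario, no treatment effect, one year of follow-up from index, stroke 1.6 and death 3.5 per 100 PY (section 9.5). Assumed: 50–80% with a pre-index record, other AF records arising after index at 0.1–0.6 per year, 70% of stroke stays coded with AF.

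- Post-index entrants made up 3–15% of the cohort.
- Stroke rate in the whole cohort: 1.73–2.01 per 100 PY.
- Death rate in the whole cohort: 3.36–3.47 per 100 PY.
- If 80% of one arm and 60% (or 50%) of the other have a pre-index record, with other records arising at 0.3 per year: stroke rate ratio 1.726/1.896 = 0.91 (or 1.726/2.014 = 0.86); death rate ratio 3.471/3.415 = 1.02 (or 3.471/3.364 = 1.03).
- Pre-index records only: stroke 1.60–1.62 and death 3.46–3.50, the input values within simulation error.

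The one-year stroke ratios lie further from 1 than the 0.94 in step 3 because a record rate of 0.3 per year means only 1 − exp(−0.3 × 0.5) = 14% acquire a non-outcome record in six months. Outcome stays are then a larger part of post-index entry.

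**The case against.** **The window has a reason.** Claims do not record the indication, and LTD registration needs a request from the general practitioner and validation by the insurer (section 9.4), so the record can lag treatment. This stands. It justifies keeping the window in some analysis, but not counting time and events from index for those patients.

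**A reader might infer that the hazard ratios are biased.** The documents do not show that. They give neither the share entering after index nor AF coding of outcome stays by arm, and section 9.9 expects the specificity of the AF definition not to differ by treatment group. That expectation does not establish equal post-index entry, but the 10% versus 20% contrast is an assumption.

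**A reader might infer that all time before the AF record is immortal.** That holds strictly only for death, and even there an in-hospital death during the qualifying stay counts. A stroke or bleeding stay without an AF code can precede a later AF record, so that time is not event-free.

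**Outcome stays may carry the AF code less often than 90%.** Section 9.4 says of associated diagnoses: "They are mainly underlying chronic diseases". It also makes their recording conditional on resource use, and 9.9 acknowledges stays where AF goes uncoded. The coding share is therefore varied down to 30% above.

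**Matching may help.** Having no pre-index AF record is a baseline feature, and section 9.3.5 feeds hospital diagnoses and other history into the hdPS. Matching could narrow an imbalance between arms. It does not remove outcome-driven entry or correct absolute rates.

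**The sensitive cohort is a partial check.** It admits some patients with unrecorded AF without needing an event, but it keeps every post-index entrant of the specific cohort.

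**Section 9.9 also says "there is no study selection bias, nor attrition bias".** That statement rests on complete extraction from a national database. It does not address the AF window and should not be read as a considered denial of this problem.

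**Conclusion.** The definition of the main cohort is wrong as written: it conditions on follow-up and contradicts the protocol's own description in 9.9. Early incidence of stroke, bleeding and ACS is biased upward and death slightly downward, whether or not the arms are alike. In the simulated scenarios the one-year stroke rate reads 1.73–2.01 instead of 1.6 per 100 PY, and death 3.36–3.47 instead of 3.5.

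For hazard ratios the bias is possible but not shown. Under the base assumptions it gives about 0.94 at one year and 0.97 at two years, the planned horizons; the six-month value of 0.90 is not a planned comparison. Other assumed inputs give one-year stroke ratios from 0.86 to 0.99, and equal shares and coding give about 1. Confidence is high for the mechanism and low for any particular hazard ratio.

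**What to change.** Reconcile section 9.3.1 and the abstract with section 9.9 by requiring definite-AF evidence on or before the index date for the main analysis. Keep the window to six months after index as a sensitivity cohort. There, patients who qualify only after index should enter at the date of the AF record, and an outcome stay should not count as the qualifying record.

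This changes the protocol wording and one cohort-building rule, and can be made before the extraction planned for Q3–Q4 2016. The cost is a smaller main cohort that loses patients whose AF or LTD is recorded only after treatment starts. Under the simulation's assumptions that is 3–15% of the cohort, against about 100 000 expected in section 9.5; the true share is not in the documents. These patients remain in the sensitivity cohort if they are still under follow-up at the record date.

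A minor, separate point: the probable-AF score uses predictors dated after index ("≥ 1 drug dispensation within 2 months before or 2 months after index date"). This affects only the sensitive cohort, and limiting the predictors to information up to index would remove it.

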9.3.2. Disease definitions for exclusion criteria

Rheumatic valve disease will be defined as a hospitalisation with rheumatic valve disease diagnosis (primary, linked or associated I05-I09 ICD-10 codes) or LTD registration for rheumatic valve disease (I05-I09 ICD-10 codes), before index date (three-year history).

Valve replacement will be defined as a hospitalisation with diagnosis-related group of valve replacement or medical procedure for valve replacement (three-year history).

Other probable indications of first anticoagulant dispensation:

- **Treatment of VTE** will be defined as index date within 2 months after hospital discharge for a pulmonary embolism (primary or associated diagnosis I26 ICD-10

code) or deep vein thrombosis (primary or associated diagnosis I80, I81, I82 ICD-10 codes);

- **Prevention of VTE after orthopaedic surgery** will be defined as index date within 2 months after hospital discharge for an orthopaedic surgery (using diagnosis-related group codes).

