9.2. SETTING

This is a study of subjects with a first dispensation of an anticoagulant (VKA or DOAC) for SPAF in a real world setting, identified and followed in the French national claims and hospital database (SNIIRAM).

Population definition

All subjects with a first reimbursed dispensation of rivaroxaban (15 or 20 mg), dabigatran (110 or 150 mg) or VKA in 2013 or 2014 will be extracted from the database. Among them, some will have clear AF diagnosis information, some an indication other than AF and other no clear information about anticoagulant indication. To overcome this obstacle, we will use two diagnosis definitions for AF, a specific definition in order to minimize the risk of false positives, and a sensitive definition in order to minimize the risk of false negatives, in such a way that two NVAF cohorts will be defined:

- **Specific NVAF cohort** (for the main analysis) will include definite NVAF subjects as defined below;
- **Sensitive NVAF cohort** (as secondary analysis) will include definite NVAF and probable NVAF subjects as defined below.

Definite NVAF subjects will be defined with all the following inclusion criteria:

- A first reimbursed dispensation of rivaroxaban, dabigatran, or VKA in 2013 or 2014, and
- No previous DOAC (rivaroxaban, dabigatran, apixaban) or VKA dispensation during the previous three years,
- Definite AF information in the database (see variable definition below),
- No other indication for the use of anticoagulant (treatment of venous thromboembolic events (VTE), prevention of VTE after orthopaedic surgery),
- No history of rheumatic valve disease or valve replacement (non-valvular AF definition from the 2012 European Society of cardiology guidelines, Camm 2012).

Probable NVAF subjects will be defined with all the following inclusion criteria:

- A first reimbursed dispensation of rivaroxaban, dabigatran, or VKA in 2013 or 2014, and
- No previous DOAC (rivaroxaban, dabigatran, apixaban) or VKA dispensation during the previous three years,
- Probable AF information in the database (using the development of an AF disease score, see variables definition below),
- No other indication for the use of anticoagulant (treatment of VTE, prevention of VTE after orthopaedic surgery),
- No history of rheumatic valve disease or valve replacement (non-valvular AF definition from the 2012 European Society of cardiology guidelines, Camm 2012).

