9.4. DATA SOURCES

The SNIIRAM database is the national healthcare insurance system database linked to the national hospital-discharge summary database (*Programme de Médicalisation des Systèmes d'Information*, PMSI) and the national death registry, using a unique pseudonymized identifier. It includes the three main healthcare insurance funds (CNAMTS³, MSA⁴, RSI⁵), which represent about 96% of the French population, and currently some of the 19 other smaller French healthcare insurances for specific professional organisations such as militaries, deputies and senators, priests, Opera... (Moulis 2015). To the extent that the SNIIRAM is a national database, all subjects are followed-up until they died. The only dropouts are subjects who leave the country to live abroad and those who join one of the smaller French healthcare insurance organisations not yet included in the SNIIRAM, which is rare and not linked with a disease or healthcare package. The SNIIRAM contains individual pseudonymised information on (Tuppin 2010, Moulis 2015):

- General characteristics: gender, year of birth, affiliation scheme, area of residence;
- Month and year of death;
- Long-term disease (LTD, or ALD in French, and associated ICD-10 codes) with starting and ending date. There is a list of 30 LTD for a total of 3448 available ICD-10 codes, which includes most of chronic diseases with long term and/or expensive treatment; e.g. a disease such as AF is specified by the ICD-10 code within LTD. Registration with a LTD is obtained at the request of a patient's general practitioner and must be validated by the health insurance system physician. Once registered, patients receive full (i.e. 100%) reimbursement for expenditure related to the LTD, as defined by the health authorities. The LTD information is specific for the diagnosis (very low risk of false positives), but not sensitive because not all patients with the disease ask to benefit from a LTD;
- Outpatient reimbursed healthcare expenditures: visits, medical procedures, medical imageries, lab tests, drugs, medical devices, transports, sick leaves... with prescriber and professional caregiver information (medical or paramedical specialty, private/public practice), dates (prescription and dispensation), and codes (but not the medical indication nor result);

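### The valve-replacement exclusion sees only an operation in the last three years, so some patients with an older, mainly biological, prosthesis are counted as non-valvular

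*Protocol*

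**What the plan says.** Section 9.2 builds both the definite and the probable non-valvular cohorts on the criterion "No history of rheumatic valve disease or valve replacement (non-valvular AF definition from the 2012 European Society of cardiology guidelines, Camm 2012"). It has no time limit.

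Section 9.3.2 turns this into data rules. Valve replacement "will be defined as a hospitalisation with diagnosis-related group of valve replacement or medical procedure for valve replacement (three-year history"). Rheumatic valve disease, in the same section, is found through hospital diagnoses in any position and also through "LTD registration for rheumatic valve disease (I05-I09 ICD-10 codes), before index date (three-year history").

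Two other provisions matter. Section 9.2 also requires "No previous DOAC (rivaroxaban, dabigatran, apixaban) or VKA dispensation during the previous three years". Section 9.1 sets the data window: "Data will be extracted from 1 January 2010 to 31 December 2015".

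On what the database can show, section 9.4 lists "Long-term disease (LTD, or ALD in French, and associated ICD-10 codes) with starting and ending date" and says of hospital coding that "Associated diagnoses can be used to define chronic diseases".

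**The concern.** A prosthetic valve is a lasting state, but the rule looks only for the event that created it, and only over three years. A patient operated on before that window leaves no trace the rule can read, even if a later hospital stay or an LTD registration records the prosthesis. The definite-AF cohort carries the main analysis, so any such patient sits in the main result as non-valvular.

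Two things would be at stake. The cohort would not quite be the population it is named for. And if prescribers favoured VKA for patients they knew to have a prosthesis, and those patients had more events, the VKA arm would look slightly worse than it should for stroke, bleeding and death. Such a bias does not shrink as the cohort grows.

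**Working it through.** The protocol states no figure on this point, so there is none to reproduce. The check has three parts.

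**1. Who passes every criterion?** Take a patient with a bioprosthesis implanted in 2007, no oral anticoagulant for three years, a hospital stay with an AF diagnosis in 2013, and a first anticoagulant dispensation in 2013.
- New user with a three-year washout (9.2): met.
- Definite AF (9.3.1): met.
- No recent VTE or orthopaedic stay (9.3.2): met.
- No replacement stay or procedure in the three-year history (9.3.2): met, because the operation was six years earlier and before the extract begins.

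The patient is classed as definite non-valvular AF. A patient with an older valve on continuing VKA fails the washout and is out. That should cover nearly all older mechanical valves, which is an inference and not a protocol statement.

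**2. Would a longer procedure look-back solve it?** Look-back available = index date minus 1 January 2010.
- Index 1 January 2013: 3.0 years.
- Index 31 December 2013: 4.0 years.
- Index 31 December 2014: 5.0 years.

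A uniform window longer than three years is not possible in this extract. Codes that record a valve already in place are the only practical route.

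**3. How large could the effect be?** Let fV and fR be the undetected shares among VKA and rivaroxaban starters, and k the event-rate ratio of these patients to true non-valvular patients. With a true hazard ratio of 1, and treating it as a simple rate ratio:

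observed HR = [1 + fR(k − 1)] / [1 + fV(k − 1)]

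All three inputs are assumptions; the protocol gives none of them.

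| fV | fR | k = 2 | k = 3 |
|---|---|---|---|
| 1% | 0 | 1/1.01 = 0.990 | 1/1.02 = 0.980 |
| 1% | 0.2% | 1.002/1.010 = 0.992 | 1.004/1.020 = 0.984 |
| 2% | 0 | 1/1.02 = 0.980 | 1/1.04 = 0.962 |
| 2% | 0.5% | 1.005/1.020 = 0.985 | 1.010/1.040 = 0.971 |
| 5% | 1% | 1.01/1.05 = 0.962 | 1.02/1.10 = 0.927 |

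If fV = fR, the ratio is 1 whatever k is. With fV at or below 2% and k of 2 to 3, the shift is 0 to about 4%. The 5% row is an outer case. None of the rows allows for what the hdPS removes.

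**The case against.** **The washout.** A reader might infer that patients with older prosthetic valves in general enter the cohort. They do not: the three-year VKA/DOAC washout takes out anyone on continuing VKA. This stands, and it narrows the point to older, mainly biological, valves without recent anticoagulation.

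**Direction.** A reader might also infer that the leak falls mostly in the VKA arm and so favours rivaroxaban. The protocol contains nothing on how many such patients there are, how they split by drug, or how their event rate compares. Channelling to VKA is plausible but assumed. This stands.

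**The hdPS.** It would be wrong to say the score could catch these patients only by luck. Section 9.3.5 feeds it other LTD registrations, one-year hospital diagnoses in any position, and three-year drug classes and healthcare use. A recorded prosthesis that strongly predicted VKA would also tend to push a patient to the edge of the score (outliers, 9.7.3) or outside the matching caliper (9.7.4). Partial offset is therefore likely, though a rare code may not be selected, and hospital diagnoses from the second and third year back are not read. This stands in large part.

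**Size.** For 20 000 per group, the table in 9.5 gives the hazard ratio below 1 whose interval excludes 1 as 0.82 at 2% incidence and 0.89 at 5%. A shift of up to 4% is small beside that. This stands.

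**A matter for the SAP.** Section 9.6 leaves the detail of disease definitions to the SAP, and three years is the protocol's usual look-back. But 9.3.2 already fixes which kinds of record count and over what period, so an SAP that follows it keeps the gap. The limitations in 9.9 do not cover it either: they argue equal misclassification between arms only for the AF definition and do not mention prosthetic valves. This objection fails.

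**Conclusion.** The rule in 9.3.2 does not fully deliver the criterion in 9.2. As written, it admits patients with an older prosthesis, mainly biological, who have had no oral anticoagulant for three years and then start one with definite AF. That much follows from the text alone.

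The consequence for the results is conditional and probably small. If these patients are channelled to VKA, make up no more than 2% of VKA starters and have 2 to 3 times the event rate, the rivaroxaban-VKA hazard ratio moves towards rivaroxaban by about 0 to 4% before any correction by the hdPS. With equal shares there is no bias. On the same channelling assumption, rivaroxaban versus dabigatran is probably little affected. The documents do not support a claim that the main comparison is materially biased. They do support a cheap repair to the definition.

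**What to change.** In section 9.3.2, keep the diagnosis-related group and procedure codes for valve replacement and add a second route. Exclude anyone with a hospital diagnosis (primary, linked or associated) in the three-year history, or an LTD active at index, that codes presence of a prosthetic heart valve (ICD-10 Z95.2-Z95.4). Carry the codes into the data extraction plan before it is approved. In the flow chart of 9.7.5, report the number excluded by this route for each index drug. That count would show how the recorded cases split between the drugs, where at present there is only assumption.

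The cost is a few extra codes and a slightly smaller cohort, using sources section 9.4 already describes. Capture will be incomplete. Section 9.4 says associated diagnoses are recorded when they represent specific healthcare resources, so a prosthesis may go uncoded, and the protocol does not show whether these codes occur in LTD registrations. The yield is therefore uncertain, and the limitations in 9.9 should say so in a sentence.
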